- Treatment will continue until disease progression, unacceptable treatment-related toxicity, or participant or physician decision to discontinue.
- Participants discontinuing study intervention will return for a short-term follow-up visit (Visit 801) 30 days (± 14 days) after discontinuation of all study treatments.
- Long-term follow-up begins the day after the short-term follow-up visit and continues until participant's death, withdrawal from study, or study completion. Long-term follow-up visits should occur approximately every 2-3 months (Q60-90D). For participants without disease progression at treatment discontinuation, tumor assessments should occur approximately every 3 months.

Study Population:

Participants have Ewing's sarcoma or Ewing's sarcoma-like tumor that has not responded to previous treatment or has returned, are 1 to <40 years old, are ≥ 10 kg, and have a life expectancy of at least 8 weeks. Participants must be able to swallow and/or have a gastric/nasogastric tube. If on systemic steroids at study entry, the dose must be stable or decreasing during the 7 days prior to Cycle 1 Day 1.

Intervention Groups and Duration:

All participants will come to the investigative site on Day 1 to 5 of each 21-day cycle to receive:

- Irinotecan IV infusion
- Temozolomide capsules

Arm A participants will also take abemaciclib orally twice daily during each 21-day cycle.

Additional evaluations on Day 8 and Day 15 of each cycle will be conducted either at the study site, remotely (that is, by telephone, IT-assisted virtual visit, mobile healthcare, or a combination thereof) at the direction of the sponsor, according to local laws and regulations.

Ethical Considerations of Benefit/Risk:

[figure not shown]
The safety and efficacy profile for combination of abemaciclib, irinotecan, and temozolomide supports the overall benefit/risk profile. This combination was tolerable in Part A of Study JPCS in pediatric participants with relapsed or refractory solid tumors. Considering the measures to minimize risk, including frequent assessments by the medical team including monitoring of

hematologic and hepatic laboratory values, and the potential benefit of disease control, the benefit/risk profile is considered favorable for this patient population.

Data Monitoring Committee: Yes (Independent DMC).

Overall Design:

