3.2. Schedule of Activities

This section includes the following SoA:

- Screening, Treatment, and Post-Discontinuation Follow-Up SoA for all participants
- Continued-Access SoA for participants on abemaciclib (See Section 7.8.1 of the CAMPFIRE Master Protocol for additional details)

Overview

The windows for the SoA and administration of first dose are based on calendar days.

At any time in the study, laboratory and pregnancy tests may be collected at a local clinic in accordance with local laws and regulations if deemed appropriate by the investigator. All results should be reviewed and recorded in the eCRF. A virtual visit with the study investigator is not required for a local lab draw or pregnancy test.

Screening and Baseline

The screening period allows up to 28 days for confirmation of eligibility and completion of baseline assessments.

Treatment Period

Cycles are 21 days. During the on-study treatment period, participants will return to clinic on Days 1-5 for IV infusions. Additional evaluations on Day 8 and Day 15 of each cycle will be conducted on-site, remotely (that is, by telephone, IT-assisted virtual visit, mobile healthcare, or a combination thereof) or a combination of remote and on-site at the direction of the sponsor, according to local laws and regulations.

Treatment will continue until disease progression, unacceptable treatment-related toxicity, or participant or physician decision to discontinue.

Tumor Response

Tumor response per RECIST 1.1 should be assessed approximately every 2 cycles (at Cycles 3 and 5) and then every 3 cycles (beginning Cycle 8) until the participant has objective disease progression, death, or study completion.

Short- and Long-Term Follow-Up

Participants discontinuing study intervention will return for a short-term follow-up visit (Visit 801). The short-term follow-up visit will take place 30 days (± 14 days) after the decision is made to discontinue all study treatment.

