Poststudy treatment and anticancer therapy information	X ^b	X	
 Telephone assessment is acceptable. For all participants, details on subsequent anticancer treatment (start/stop dates and treatments administered)
Height, weight	X ^b		
Vital signs	X ^b		
 Measure temperature, blood pressure, pulse rate, and respiratory rate
Physical examination	X ^b		
 Include respiratory auscultation
CCI	X ^b		CCI
CCI	X		CCI
Performance status	X ^b		
 Lansky for age <16 years Karnofsky for age ≥16 years

	Short-Term Follow-Up ^a	Long-Term Follow-Up ^d	
Visit	801	802-8XX	
Visit Interval Tolerance (Days)	CCI		
Procedure			Instructions
Tumor imaging	X	X	
 • According to RECIST 1.1 • No longer required after objective PD • Obtain within 4-6 weeks of treatment discontinuation due to clinical (not objectively confirmed) PD • V801 scan is not required if treatment discontinuation was not due to PD and the most recent scan prior to discontinuation was <90 days. LTFU scan interval should remain every 60-90 days until objective PD • CT scans of the chest, abdomen, pelvis, and the site of the known lesion if located elsewhere • Same modality used at baseline should be used throughout study • See Section 3.9.1 for additional guidance
Hematology	X ^c		See Attachment 2 for sample collection guidance
Clinical chemistry	X ^c		See Attachment 2 for sample collection guidance
Exploratory biomarkers (plasma sample)	See Attachment 2 and Attachment 3 for sample collection guidance		Only for participants who did not have a sample collected at the time of disease progression or at the time when study treatment was discontinued

Abbreviations: AE = adverse event; BSA = body surface area; CT = computed tomography; CTCAE = Common Terminology Criteria for Adverse Events (NCI 2017); CCI; CCI; LTFU = long-term follow-up; CCI; PD = progressive disease; RECIST 1.1 = Response Evaluation Criteria in Solid Tumors, Version 1.1.

- ^a Short-term follow-up begins the day after the participant and the investigator agree that the participant will no longer continue study treatment and lasts approximately 30 days. In all cases, no follow-up procedures will be performed for a participant who withdraws informed consent unless he or she has explicitly provided permission and consent.

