Attachment 5. Protocol JP04 Addendum Restricted and Prohibited Concomitant Therapy

This attachment describes medications, treatments, and drug classes restricted or prohibited, with exceptions and conditions for use during the study treatment period (there are no prohibited therapies during the follow-up period). Participants who, in the assessment by the investigator, require the use of any of the prohibited treatments for clinical management should be removed from the trial. Participants may receive other supportive therapy or vaccinations that the investigator deems to be medically necessary.

Vaccine Guidance

Live vaccines are not permitted while on treatment and for at least 3 months after the last dose of abemaciclib.

Guidance for Modulators of CYP3A

Abemaciclib is extensively metabolized through oxidation by CYP3A. In clinical drug interaction studies,

- coadministration of clarithromycin, a strong CYP3A inhibitor, increased exposure (AUC) of abemaciclib by 3.4-fold (Study I3Y-MC-JPBE), and
- coadministration of rifampin, a strong CYP3A inducer, decreased exposure of abemaciclib by 95% (Study I3Y-MC-JPBF).

Strong inhibitors of CYP3A (given via non-topical routes of administration) should be substituted or avoided if possible (see list below). This includes grapefruit or grapefruit juice. In particular, avoid oral administration of the very strong CYP3A inhibitor, ketoconazole.

If coadministration with a strong CYP3A inhibitor is unavoidable, investigators should reduce the dose of abemaciclib according to the dose reduction table in Section 3.7.8.3. For participants receiving the original starting dose, the dose should be reduced to the first dose reduction level. For participants who have already had a dose reduction for tolerability, reduce the dose further to the second dose reduction level. For subjects receiving doses which do not have an appropriate dose reduction option, or who have already been dose reduced to the lowest possible dose level, the investigator may consider suspending abemaciclib for the duration of the strong CYP3A inhibitor medication. Dose suspensions ≥ 21 days must be discussed with Lilly CRP/CRS.

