7.9.2. Adverse Events

The MedDRA Version 21.0 (or higher) will be used to map reported AEs to MedDRA terms. The MedDRA LLT will be used in the treatment-emergent computation. PTs identified as clinically identical or synonymous may be grouped together under a single consolidated PT. For

example, ‘Neutropenia’ and ‘Neutrophil count decreased’ may be aggregated and reported as ‘Neutropenia.’ The NCI CTCAE version 5.0 will serve as the reference document for grading the severity of all AEs and other symptoms.

Pre-existing conditions are defined as AEs that begin prior to the first dose of study treatment.

A TEAE is defined as any AE that begins between the day of first dose and 30 days after treatment discontinuation (or up to any time if serious and related to study treatment), or any preexisting condition that increases in CTCAE grade between the day of first dose and 30 days after treatment discontinuation (or up to any time if serious and related to study treatment). Comparisons of preexisting conditions to on-treatment events at the LLT level will be used in the treatment-emergent computation.

A SAE is any AE during this study that results in one of the following outcomes: death, initial or prolonged inpatient hospitalization, a life-threatening experience (that is, immediate risk of dying), persistent or significant disability/incapacity, congenital anomaly/birth defect, or considered significant by the investigator for any other reason. Additionally, important medical events that may not result in death, be life-threatening, or require hospitalization may be considered SAEs when, based on appropriate medical judgment, they may jeopardize the patient and may require medical or surgical intervention to prevent 1 of the outcomes listed in this definition.

Treatment-emergent adverse events will be summarized by SOC and by decreasing frequency of PT within SOC.

Safety analyses will include summaries of the following:

- AEs, including severity and possible relationship to study drug
- SAEs, including possible relationship to study drug
- AEs leading to dose adjustments
- discontinuations from study treatment due to AEs or death
- treatment-emergent abnormal changes in laboratory values
- treatment-emergent abnormal changes in vital signs.

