7.9.4. Clinical Laboratory Evaluation

All relevant hematology and chemistry laboratory values will be graded according to CTCAE version 5. These calculated grades will be summarized by maximum postbaseline grade over the entire study for each treatment arm. Treatment-emergent changes will be summarized by the

maximum postbaseline grade, and a shift table of baseline grade by maximum postbaseline grade will be produced.

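### The worst laboratory grade has no cut at the start of new anticancer therapy, so non-study-drug toxicity may enter the tables and distort the arm comparison in either direction

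*SAP*

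**What the plan says.** SAP 7.9.4 states: "These calculated grades will be summarized by maximum postbaseline grade over the entire study for each treatment arm". Its next sentence bases the treatment-emergent changes on the "maximum postbaseline grade, and a shift table of baseline grade by maximum postbaseline grade will be produced". Neither sentence gives an end date or a rule for values taken after another anticancer therapy has started.

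SAP 7.9.2 does bound adverse events. A TEAE begins, or a pre-existing condition worsens, "between the day of first dose and 30 days after treatment discontinuation". The limit is lifted only for events that are both serious and related to study treatment.

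On timing, the protocol Synopsis places Visit 801 "30 days (± 14 days) after discontinuation of all study treatments", while the text of Section 3.2 places it "30 days (± 14 days) after the decision is made to discontinue all study treatment". Table JP04.3 schedules hematology and chemistry at Visit 801 and not in long-term follow-up. The same table collects start and stop dates of subsequent anticancer treatment from Visit 801 onwards. Protocol 3.7.6 bars other chemotherapy only during study treatment, and Attachment 5 adds that "there are no prohibited therapies during the follow-up period".

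Protocol 3.10.3.2 also refers to Master Protocol Section 10.3.1 for details of the safety analysis. That document was not available for this review.

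**The concern.** Laboratory abnormalities belong to the secondary safety endpoint. Protocol 3.3.3 lists neutropenia, thrombocytopenia and hepatotoxicity among the most significant overlapping risks of the three drugs. The laboratory grade tables are the objective record of these.

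A maximum can only rise. Suppose a participant stops study treatment, starts another cytotoxic regimen and has the Visit 801 blood drawn during its nadir. That grade can become the participant's worst grade and be reported under the randomized regimen. The SAP plans summaries of adverse events by possible relationship to study drug but no equivalent for graded laboratory values, so a reader of the table could not separate such a value out.

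There is also a mismatch that needs no assumption about later therapy: the adverse event and laboratory tables cover different periods.

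**Working it through.** The plan states no laboratory grade rate or between-arm difference, so there is no figure to reproduce. The timing comes from the documents. The rates below are assumptions.

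**1. Window.** 30 − 14 = 16 and 30 + 14 = 44, so Visit 801 falls on days 16 to 44. The TEAE window closes at day 30. A draw on days 31 to 44 therefore enters the laboratory maximum, while a non-serious adverse event starting on the same day is not a TEAE. The day count is exact from discontinuation under the Synopsis. Under the Section 3.2 text it runs from the decision to stop.

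**2. Exposure.** On treatment there are three scheduled draws per cycle (Days 1, 8 and 15; Table JP04.2 lets sites drop Days 8 and 15 only after Cycle 3). In follow-up there is one. Visit 801 changes the table only if new therapy has begun, the draw catches its toxicity, and the grade exceeds every earlier one.

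**3. Formula.** Let p be the proportion with Grade 3-4 on study drugs. Let q be the chance that a participant without such a grade newly shows one at Visit 801 because of the next therapy.

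- Reported rate = p + (1 − p)q
- Equal q in both arms: reported difference = (1 − q)(pA − pB)
- Unequal q: reported difference = (pA − pB) + (1 − pA)qA − (1 − pB)qB

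**4. Equal contamination.** Assume pA = 60% and pB = 30%, a true difference of 30 points. SAP 6.1.2 plans at least 45 participants randomized 2:1, so about 30 and 15.

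| q, both arms | Arm A | Arm B | Difference | Extra participants A / B |
|---|---|---|---|---|
| 2% | 60.8% | 31.4% | 29.4 | 0.2 / 0.2 |
| 10% | 64.0% | 37.0% | 27.0 | 1.2 / 1.05 |
| 25% | 70.0% | 47.5% | 22.5 | 3.0 / 2.6 |

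For scale, q is the share already on new therapy at the draw times the chance that the draw newly shows Grade 3-4: 10% × 20% = 2%, and 50% × 50% = 25%.

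**5. Unequal contamination, same p.**

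- qA = 5%, qB = 15%: 62.0% − 40.5% = 21.5 points (narrower).
- qA = 15%, qB = 5%: 66.0% − 33.5% = 32.5 points (wider).
- The difference widens once qA/qB exceeds (1 − pB)/(1 − pA) = 0.70/0.40 = 1.75.
- With no true difference (50% in both arms), qA = 25% and qB = 10% give 62.5% − 55.0% = 7.5 points, which is spurious.

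**6. Precision.** The 95% half-width around 60% versus 30% is 1.96 × √(0.60 × 0.40/30 + 0.30 × 0.70/15) = 1.96 × √0.022 ≈ 29 points.

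**The case against.** The strongest reply is that the effect is small and the tables are descriptive. At q = 10% about one participant per arm is reclassified, and 3 points is slight against a half-width of about 29. No test of laboratory grades is planned, and SAP 7.12.1 sets no safety stopping rule that they could trigger. This stands and makes the point minor.

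A second reply is that the whole-study phrase is attached only to the first summary in 7.9.4. The protocol's TEAE definition speaks of a defined treatment period, so the treatment-emergent laboratory summary might be meant as on-treatment. That reading is open, but 7.9.4 does not state it, and the shift table uses the same unbounded maximum. Master Protocol Section 10.3.1 might supply a window; if so, it would need reconciling with the wording of 7.9.4.

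A third reply is that a whole-study maximum is a conservative safety convention, and that a draw as early as day 16 can still reflect the study drugs. This is fair. It is why Visit 801 should stay in the main analysis and the whole-study table should be kept.

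A fourth reply is that the TEAE definition has no cut at new therapy either, so cutting laboratory values alone would create a new mismatch. This also stands, and the fix allows for it.

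**Conclusion.** The concern holds as a minor one. As written, 7.9.4 can credit toxicity of a non-study drug to a randomized arm, and its window does not match the one in 7.9.2. Laboratory toxicity can be overstated, and the descriptive comparison can be distorted.

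A reader might infer that the open window necessarily shrinks the between-arm difference and so hides added abemaciclib toxicity. The documents do not support that. Shrinkage, by the factor 1 − q, follows when q is equal in both arms. Heavier contamination of Arm B shrinks the difference further, while sufficiently heavier contamination of Arm A widens it. A loss of about a third, such as 30 to 21.5 points, needs a strong imbalance against Arm B. Nothing in the documents establishes one, and the mirror-image assumption gives 32.5. Nor do the documents show that contamination will occur, only that it may.

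The central illustration is 30 points reported as 27 at q = 10%. The 60% and 30% rates and every value of q are assumptions. Unscheduled laboratory values after new therapy could add to the effect.

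**What to change.** In SAP 7.9.4:

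- Base the main maximum-grade, treatment-emergent and shift tables on values from first dose through Visit 801, excluding values on or after the start date of the first subsequent anticancer therapy.
- State how this window relates to the 30-day TEAE window in 7.9.2. A strict 30-day cut is not advised, because it would discard protocol-compliant Visit 801 draws on days 31 to 44.
- Flag TEAEs that start after new therapy in the same way, so that the adverse event and laboratory tables can be read together.
- Keep the whole-study maximum as a supplementary table.

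The protocol's two starting points for the Visit 801 count should also be reconciled, so that the window has one definition.

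The cost is a few sentences in the SAP and one flag in programming. The dates of subsequent therapy are already collected, and trial conduct does not change. The downside is that a late study-drug effect first seen after new therapy starts would appear only in the supplementary table.

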7.9.5. Vital Signs and Other Physical Findings

Temperature, blood pressure, pulse rate, weight, BSA, and Lansky/Karnofsky Performance Status will be summarized by cycle, including a summary of treatment-emergent abnormal changes.

7.9.6. Electrocardiograms

Electrocardiograms (ECGs) are scheduled to be performed. A listing of ECG findings at baseline and unscheduled postbaseline visits that are considered to be a medical history condition or an AE will be provided. Other analyses may also be done as appropriate.

7.10. Subgroup Analyses

Due to sample-size limitations, no formal statistical tests of treatment effect by subgroup will be prespecified. However, descriptive statistics for primary and secondary efficacy measures will be provided by treatment arm within the randomization strata and the following subgroups:

- Disease Status (relapsed vs refractory)
- Prior irinotecan and/or temozolomide
- Gender
- Race
- Original disease location (axial vs not)

7.11. Protocol Violations

Important protocol deviations that potentially compromise the data integrity and patients' safety will be listed. These deviations will include those defined by:

- Informed consent
- Inclusion/exclusion criteria
- Investigational product
- Study procedures
- Administrative/oversight
- Safety
- Other

On the basis of the discussion with the study team, the detailed description of each deviation within the above category and the method to identify each deviation will be listed in a separate document – Business Process Document: Important Protocol Deviations.

7.12. Interim Analyses

Only the DMC is authorized to evaluate aggregate unblinded interim efficacy and safety analyses. Blinding and unblinding details are specified in a separate blinding and unblinding plan document.

7.12.1. Safety Interim Analyses

The DMC is responsible for providing external oversight of participant safety in Study JP04 independently of the Lilly study team and Lilly Global Patient Safety.

Safety interim analyses will be reviewed by the DMC at a frequency described in the DMC charter, but no less than approximately every 6 months while participants are still in the on-study treatment period. The safety interim analyses will be conducted to evaluate the overall safety profile of abemaciclib when given in combination with irinotecan and temozolomide.

At each safety interim analysis, the DMC may recommend that the trial continue without modifications, continue with specific modifications, or be stopped for safety concerns. There will be no prespecified rules for stopping the trial due to safety concerns. The DMC members will review safety data at each safety interim analysis. If a significant safety signal is identified, the DMC may recommend a protocol amendment, termination of enrollment, and/or termination of study treatment. The recommendations of the DMC will be communicated to the Lilly Senior Management Designee and, if necessary, an Internal Review Committee. Further details on the members, activities, and responsibilities of the DMC can be found in the DMC charter.

7.12.2. Futility Analysis

One futility analysis is planned after approximately ^{CC} PFS events have been observed. If the observed HR of PFS by investigator assessment is ^{CCI}, the DMC should recommend that the study be stopped for futility. This analysis will rely on a frequentist analysis of PFS. The Bayesian analysis method used at primary analysis will not be utilized for the futility analysis, nor will PFS by BIRC be considered at the futility analysis.

7.13. Annual Report Analyses

Annual report analyses, including Developmental Safety Update Report and Investigator's Brochure analyses, are described in the LY2835219 Program SAP.

7.14. Clinical Trial Registry Analyses

Additional analyses will be performed for the purpose of fulfilling the CTR requirements.

Analyses provided for the CTR requirements include the following:

- Summary of AEs, provided as a dataset which will be converted to an XML file. Both SAEs and 'Other' AEs will be summarized by MedDRA PT within treatment group.
- An AE is considered 'Serious' whether or not it is a TEAE.

- An AE is considered in the ‘Other’ category if it is both a TEAE and is not serious. For each SAE and ‘Other’ AE, for each term and treatment group, the following are provided:
 - the number of participants at risk of an event
 - the number of participants who experienced each event term
 - the number of events experienced
- Consistent with www.ClinicalTrials.gov requirements, ‘Other’ AEs that occur in <5% of patients/subjects in every treatment group may not be included if a 5% threshold is chosen (5% is the minimum threshold).
- AE reporting is consistent with other document disclosures (e.g., the CSR, manuscripts, and so forth).

In addition, a participant flow will be created that will describe how many enrolled patients completed the study, and for those who did not, the frequency of each reason for not completing. This analysis will be based on study discontinuation, not treatment discontinuation. A patient will be identified as having completed the study if the patient has received ≥ 1 dose of study drug and have ≥ 1 postbaseline tumor assessment at the time of the final analysis.

8. References

- Cox DR. Regression models and life-tables. *J Royal Stat Soc Ser B*. 1972;34(2):187-220. <https://doi.org/10.1111/j.2517-6161.1972.tb00899.x>

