After the short-term follow-up visit, all participants will enter the long-term follow-up period (Visit 802-8XX). Long-term follow-up begins the day after the short-term follow-up visit is completed and continues until participant's death, withdrawal from study, or study completion. Long-term follow-up visits should occur approximately every 2-3 months (Q60-90D). Tumor assessments should continue approximately every 3 months during follow-up for participants without evidence of disease progression at the time of treatment discontinuation.

Table JP04.1. Baseline Schedule of Activities

Procedure	Day relative to C1D1		Instructions
	≤28	≤14	
Informed consent	X		
 Must be signed prior to conducting any protocol-specific tests/procedures Minor participants must be re-consented if they reach the age of majority during the course of the study.
Inclusion/exclusion criteria	X		
 Confirm prior to randomization
Randomization	X		
Demographics	X		
 Include race, gender, ethnicity, and birth date per local regulations.
Preexisting conditions and medical history, including relevant surgical history	X		
 Include Ewing's sarcoma or Ewing's sarcoma-like fusion genes, if known CCI
Prior and current treatments for Ewing's sarcoma	X		
 Record prior anticancer therapy
Substance use (alcohol and tobacco)	X		
Concomitant medications	X		
 Record all premedication, supportive care, and concomitant medication See Section 3.7.6
Adverse events	X		
 CTCAE Version 5.0
Height, weight, and body surface area	X		
Vital signs	X		
 Temperature, blood pressure, pulse rate, and respiratory rate
Physical examination	X		
 Includes respiratory auscultation
CCI	X		
 CCI
Performance status	X		
 Lansky for age <16 years Karnofsky for age ≥16 years

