7.2. Patient Disposition

A detailed description of patient disposition will be provided. It will include a summary of the number and percentage of screened patients randomized in the study, reasons for discontinuation from study treatment, and reasons for discontinuation from the study. Reason for discontinuation from both study treatment and the study will be listed by the predetermined categories. For treatment discontinuation, these include progressive disease, AE, death, withdrawal by subject, physician decision, noncompliance with study drug, protocol deviation, study terminated by the IRB/ERB/sponsor, lost to follow-up; for study discontinuation, these include study terminated by sponsor, withdrawal by subject, lost to follow-up, death. If the reason for discontinuation is AE or death, the associated AE or cause of death will be reported. The disposition will also be listed. All patients randomized in the study will be included in the summaries and listings.

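### SAP 7.14 says the registry participant flow rests on study discontinuation, but it defines completion as one dose plus one post-baseline scan, so later withdrawals and losses appear as completers (a minor reporting error)

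*SAP*

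**What the plan says.** SAP 7.14 plans a registry participant flow giving the number of enrolled patients who completed the study and, "for those who did not, the frequency of each reason for not completing". It states the basis: "This analysis will be based on study discontinuation, not treatment discontinuation". The next sentence sets the completion rule: "A patient will be identified as having completed the study if the patient has received ≥ 1 dose of study drug". The full condition is to have "received ≥ 1 dose of study drug and have ≥ 1 postbaseline tumor assessment at the time of the final analysis".

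SAP 7.2 describes the general disposition summary. It covers all randomized patients and names the categories: "for study discontinuation, these include study terminated by sponsor, withdrawal by subject, lost to follow-up, death".

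Two protocol statements give context. In Protocol 3.2, long-term follow-up "continues until participant's death, withdrawal from study, or study completion". The same section times tumor assessments by cycle, with the first on-treatment assessment at Cycle 3, and says "Cycles are 21 days".

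**The concern.** Within SAP 7.14, one sentence bases the flow on whether a participant left the study, and the next decides completion without asking that question. Withdrawal, loss to follow-up and death do not enter the rule, and reasons are tabulated only for non-completers. A participant who is dosed, scanned once and then leaves therefore appears as a completer, and the reason for leaving disappears from the flow.

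The same participant is discontinued from the study under SAP 7.2, so the trial would issue two disposition accounts that disagree. Deaths are also handled inconsistently: the same outcome is completion or non-completion depending on whether a scan preceded it.

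What is at stake is the accuracy of a public retention figure. The trial is open-label and allocates 2:1. At the minimum of 45 participants the control arm has about 15, so each control participant lost is 1/15 = 6.7% of that arm. A reader of the registry record would see none of the losses that follow a first scan.

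**Working it through.** The documents give no completion or attrition figure to reproduce. The check is to set the two rules side by side, then time the scan that triggers completion.

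**Classification under each section**

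| Participant's course | SAP 7.14 flow | SAP 7.2 disposition |
|---|---|---|
| Dosed, scanned, then withdraws | Completed, no reason shown | Discontinued: withdrawal |
| Dosed, scanned, then lost | Completed, no reason shown | Discontinued: lost to follow-up |
| Dosed, scanned, then dies | Completed | Discontinued: death |
| Dosed, dies before any post-baseline scan | Not completed | Discontinued: death |
| Dosed, withdraws or is lost before any post-baseline scan | Not completed | Discontinued, with that reason |

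The sections disagree in the first three rows and agree in the last two. A randomized participant who is never dosed is always a non-completer under 7.14.

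**Timing of the trigger**

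- Inputs: first scheduled scan at Cycle 3 and 21-day cycles (Protocol 3.2).
- Cycle 3 Day 1 comes 2 × 21 = 42 days after Cycle 1 Day 1, that is, Day 43, or 42/7 = 6 weeks.
- Protocol 3.5.1.1 allows treatment to be suspended for up to 21 days for toxicity. One such delay moves the scan to (42 + 21)/7 = 9 weeks, and two move it to 12 weeks.
- SAP 7.7.2 plans OS rates at 1, 2 and 3 years. Six weeks is 6/52.18 = 11% of the first year and about 4% of three years.

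**Illustration of size: withdrawals and losses**

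The 12-month loss proportion d is assumed, since the documents give none. Take N = 45, a constant hazard h = −ln(1 − d) per year, everyone still present at day 42 scanned on time, and no competing events. The proportion lost before day 42 is 1 − exp(−h × 42/365.25).

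| Assumed d | Lost in 12 months (45 × d) | Lost before day 42 | Lost later, shown as completers |
|---|---|---|---|
| 5% | 2.25 | 0.26 | 1.99 |
| 10% | 4.50 | 0.54 | 3.96 |
| 20% | 9.00 | 1.14 | 7.86 |
| 30% | 13.50 | 1.81 | 11.69 |

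About 87% to 88% of losses in the first year fall after the first scan and would be reported as completion.

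**Illustration of size: early deaths**

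Under exponential survival, P(death before day 42) = 1 − exp(−ln 2 × (42/30.4375)/median). Protocol 3.3.1 cites a published median survival of 7 months after progression; 12 and 18 months are assumed alternatives. The probabilities are 12.8%, 7.7% and 5.2%, or 5.7, 3.4 and 2.3 of 45. These would be non-completers, while later deaths would be completers. The 7-month figure is background literature, not a projection for this trial.

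**The case against.** The best defense is scope. The rule governs one registry output. SAP 7.2 still calls for reasons for study discontinuation across all randomized patients, in summaries and listings. The analysis sets (SAP 7.1.1), PFS censoring (SAP Table JP04.7.1) and OS censoring (SAP 7.7.2) make no use of the completion flag. This stands, and it sets the severity. One qualification is that SAP 7.2 does not say its summary is by arm.

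A reader might draw several stronger conclusions that the documents do not support:

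- *Everyone who leaves after week 6 is a completer.* The trigger is a scan, not a date. Someone lost at week 8 with a delayed or missed scan is a non-completer; someone with an earlier unscheduled scan is a completer.
- *Differential loss would be concealed and the censoring biased.* The flag does not alter censoring, and SAP 7.2 still records the losses.
- *Counting early deaths as non-completion contradicts SAP 7.2.* It agrees with 7.2, which lists death as discontinuation. The mismatch lies with deaths after a scan.
- *A death before the first scan always gives a full PFS outcome.* Under SAP Table JP04.7.1, a death after two scan intervals with no adequate post-baseline assessment is censored at randomization, as is anyone without a baseline assessment.
- *The protocol defines individual completion differently.* Protocol 3.2 sets how long follow-up lasts, and Protocol 3.5.3 defines study completion as a study-level date. Neither defines a participant who has completed.

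The scope defense does not remove the contradiction inside SAP 7.14, nor the conflict with 7.2 for participants who leave or die after a scan.

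**Conclusion.** The completion rule in SAP 7.14 is wrong as written. It departs from the basis that the section itself states, and it classifies post-scan withdrawals, losses and deaths differently from SAP 7.2. These conclusions follow from the text and need no assumed figure.

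The consequence is minor: one registry table would overstate retention and omit reasons for leaving. No estimate, test or decision rule changes. The size is unknown because no attrition rate is given. The range of roughly 2 to 12 of 45 rests on assumed losses of 5% to 30% over 12 months, a constant hazard, on-time scans and no competing events.

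**What to change.** Replace the completer sentence in SAP 7.14 with a rule based on study status:

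- Withdrawal by subject, loss to follow-up and termination by the sponsor before study completion count as not completed. Give reasons by arm for all randomized participants, including those never dosed.
- State one convention for death that does not depend on scan timing, and apply it in both 7.2 and 7.14. Either keep death as a discontinuation reason, as 7.2 does now, or amend both sections to count it as completion. The second option should not be presented as existing 7.2 logic.
- Derive both tables from the same variable.

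The cost is SAP wording and one derived variable, with an edit to 7.2 as well if death is to count as completion. The downside is that the reported completion rate may be less favorable.
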